1.2 Aim 2 Objective

Conduct a pilot test of the adapted protocols and intervention in a sample of 30 CNAs from 2 similarly rated and structured community NHs to reexamine feasibility and acceptability, identify trends in key intermediate and long-term outcomes, and estimate effect size in preparation for a future randomized trial.

- A.** Evaluate the fidelity and immediate impact of the modified training by measuring (a) training attendance; (b) satisfaction with the training; and (c) pre-and post-training measures of self-compassion, perceived stress, job satisfaction, job burnout symptoms, and attitudes towards persons with dementia.
- B.** Evaluate the sustained impact of the training by comparing baseline, 3-and 6-month post-training measurements of: intent to leave job, self-compassion, perceived stress, job satisfaction, job burnout symptoms, and attitudes towards persons with dementia.

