3 STUDY DESIGN

This is a single-arm feasibility trial that will refine an existing MSC intervention in preparation for a future, randomized controlled trial with the primary goal of improving CNA job retention. We will recruit 15 CNAs from a single nursing home (NH), pilot the 8-week intervention, and collect feedback via questionnaires, interviews and a semi-structured focus group at the end of the course. Data from this cohort will be used to refine study protocols and course structure/materials for maximum feasibility and acceptability. A refined intervention will subsequently be tested in 30 CNAs from two NH settings (15 CNAs per home), with pre, post, and follow-up measurements of stress, burnout, self-compassion, job satisfaction, attitudes towards dementia, and intent to leave their job.

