- B. The second consent process will be with all participants' who are committed to joining the intervention program. Throughout the recruitment process, participants will be able to sign up on an interest sheet to indicate their interest. These participants will be able to sign up physically, during the recruitment sessions, or reach out directly to study staff to have their name included on the interest sheet. Once CNAs have expressed interest, the study staff will reach out to them one-on-one through their preferred method of communication (telephone, text, or email), and verify their commitment to the program.

Once commitment and eligibility have been confirmed, study staff will set up one-on-one meetings with participants in order to review the written consent form. This will take place up to 2 weeks before the start date of the program. During these in-person meetings, study staff will review the consent form with participants and answer any questions they may have. Additionally, study staff will ensure participants have their own copy of the consent form for their files. Once collected, all physical consent forms will be kept in a locked office in the Cecil G. Sheps Center for Health Services Research, where only study staff will have access.

Screening

This study will take up to 20 CNAs per Nursing Home. If 20 or fewer CNAs are interested in the CNA Wellbeing Program, all those interested will be able to participate. However, if over 20 CNAs are interested in the program (within one Nursing Home), the Screening Questionnaire administered during the recruitment process will be used to determine the 20 CNAs with the highest scores on the Perceived Stress Scale. The study's goal is to recruit 15 CNAs per Nursing Home.

In the event that there are over 20 CNAs interested and the study is not able to accommodate all CNAs, some Mindful Self-Compassion materials will be provided to those who are not able to join the program.

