**Mindful Self-Compassion Training  
to Improve Retention, Job Satisfaction,  
and Attitudes toward Dementia among  
Long-Term Care Nursing Assistants:  
Certified Nursing Assistants' Wellbeing**

Analysis Overview. Analyses of the intervention’s effectiveness will primarily comprise tests of changes to the outcome measures (see below) from baseline at three post-baseline timepoints: (a) post-intervention, (b) a 3-month follow-up, and (c) a 6-month follow-up. All outcomes were recorded at the same time points within the same self-report survey. Thus, overall, with baseline there were four data collection time points in the study. Secondly, analyses will consider differences in effectiveness by comparing two intervention’s two approaches: (a) the 20-hour intervention delivered in one NH and (b) the 6-hour intervention delivered in two additional NHs. In addition to outcome analyses, participants’ univariate demographic and professional characteristics were calculated to describe the sample (not detailed). Missing data were not imputed, resulting in analyses using listwise deletion of participant observations without data at each time point and for each outcome. Statistical significance was set at  $p < 0.05$  throughout (two-sided) and all analyses were conducted in Stata 16.1.

Primary Outcome. The primary outcome in the study was *Change in Intent to Leave Job*. The specific question asked of participants was “How likely is it that you will leave this job in the next year?” with intent to leave specifically being defined as a “Somewhat likely” or “Very likely” response (1 = Yes) versus a “Not at all likely” response (0 = No). The analysis of the primary outcome proceeded in two steps. First, the descriptive frequencies and percentages of “Yes” and “No” response were calculated for all participants at all four data collection time points to summarize the primary outcome across participants and time. Second, tests for the statistical significance of change from baseline was determined using three sets of McNemar’s exact  $X^2$  tests compared baseline versus the three post-baseline time points. These tests were chosen as appropriate for the (a) non-parametric nature of the data and (b) paired nature of the comparison.

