
secondary outcomes across participants and time. Second, tests for the statistical significance of change from baseline was determined using three sets of either (a) Wilcoxon sign-rank tests for continuous measures or (b) McNemar's exact  $X^2$  tests for nominal measures. These tests were chosen as appropriate for the (a) non-parametric nature of the data and (b) paired nature of the comparisons. Third, change from baseline stratified by intervention approach was determined by comparing the (a) change and (b) significance of the two sub-samples (i.e., 20-hour intervention, 6-hour intervention) for the (a) PSS, (b) PROMIS, and (c) total SCS scores.

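### Intent to leave, job satisfaction, dementia attitudes and burnout have no by-version analysis, so four of the six Aim 2B outcomes get no estimate for the refined course

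*SAP*

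**What the plan says.** Protocol section 3 describes the study in these words: "This is a single-arm feasibility trial". Home 1, with a goal of 15 CNAs, receives the 8-week course. Homes 2 and 3, with a goal of 30 CNAs between them, receive the refined 6-week course. The SAP calls these the 20-hour and 6-hour interventions.

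Aim 2 (Protocol section 1.2) concerns only the refined course in the two later homes. One of its purposes is to "estimate effect size in preparation for a future randomized trial". Part B lists what is to be followed to 3 and 6 months: "intent to leave job, self-compassion, perceived stress, job satisfaction, job burnout symptoms, and attitudes towards persons with dementia".

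The SAP deals with course version in three places:

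- **Analysis Overview.** A general commitment: "Secondly, analyses will consider differences in effectiveness by comparing two" approaches, the 20-hour and the 6-hour. No outcome, estimate or test is named.
- **Primary Outcome.** "The analysis of the primary outcome proceeded in two steps". The first is frequencies and percentages for all participants at each time point. The second is McNemar's exact test of baseline against each later time point. Neither mentions version.
- **Secondary Outcomes, third step.** Change from baseline is stratified by version, but only "for the (a) PSS, (b) PROMIS, and (c) total SCS scores".

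**The concern.** The Overview makes a general promise, and the detailed steps narrow it to three scores that leave out the primary outcome. Homes 2 and 3 are the whole Aim 2 sample, so an estimate restricted to them is the Aim 2 result itself and not an optional subgroup look.

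For intent to leave, JSS, ADQ and MBI, following the stated steps gives one change from baseline across both courses. That figure equals the refined-course change only if the two courses work equally well, and the documents give no reason to assume so. The future trial is meant to improve job retention (Protocol section 3). Intent to leave is the outcome closest to that goal, and a planner who took the pooled figure as the refined-course effect could be wrong in either direction.

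**Working it through.** The documents contain no sample-size or precision calculation, so there is no stated figure to reproduce. The check has four parts.

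**1. Coverage.** Aim 2B outcomes set against the SAP's by-version step:

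| Aim 2B outcome | SAP measure | By-version step? |
|---|---|---|
| Intent to leave (primary) | Yes/No item | No |
| Self-compassion | SCS total | Yes |
| Perceived stress | PSS | Yes |
| Job satisfaction | JSS | No |
| Burnout | MBI, three subscales | No |
| Attitudes to dementia | ADQ | No |

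Two of six are covered and four are not. PROMIS depression is split by version although Aim 2 does not list it.

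**2. What pooling does.** Let D8 be the change in home 1, D6 the change in homes 2 and 3, and w home 1's share of the analysed sample.

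- Pooled change = w × D8 + (1 − w) × D6, so pooled minus refined = w × (D8 − D6).
- At the recruitment goals, w = 15/45 = 0.33.
- Protocol section 6.2.1 sets a cap: "This study will take up to 20 CNAs per Nursing Home". With 15 to 20 per home, w runs from 15/55 = 0.27 to 20/50 = 0.40.

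Illustrations for intent to leave, in percentage points (the D8 and D6 values are assumed):

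| D8 | D6 | Pooled at w = 0.33 | Pooled minus refined |
|---|---|---|---|
| 0 | −30 | −20 | +10 (8 to 12 over the range of w): refined course understated |
| −30 | 0 | −10 | −10: apparent benefit where the refined course did nothing |
| −30 | −10 | −16.7 | −6.7 |
| −20 | −20 | −20 | 0 |

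**3. Precision.** Let b and c be the proportions switching yes-to-no and no-to-yes. The approximate 95% half-width is 1.96 × √[(b + c − (b − c)²)/n]. For b = 0.20 and c = 0.10 the variance term is 0.30 − 0.01 = 0.29, and at n = 30 the half-width is 1.96 × √(0.29/30) = 0.193. In percentage points, before listwise deletion (b and c assumed):

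| b / c | n = 45 (pooled) | n = 30 (homes 2 and 3) | n = 15 (home 1) |
|---|---|---|---|
| 0.15 / 0.05 | 12.7 | 15.6 | 22.1 |
| 0.20 / 0.10 | 15.7 | 19.3 | 27.3 |
| 0.30 / 0.10 | 17.5 | 21.5 | 30.4 |

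Refined-course intervals are wider than pooled by √(45/30) = 1.22. The factor runs from √(55/40) = 1.17 to √(50/30) = 1.29 across 15 to 20 per home. These are large-sample figures that treat CNAs taught in the same group as independent.

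**4. Why not significance tests by version.** With m discordant pairs all in one direction, the smallest two-sided exact McNemar p is 2 × 0.5^m. Five pairs give 0.063 and six give 0.031. Among 15 CNAs in home 1, at least six would have to switch, all the same way, to reach p < 0.05.

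**The case against.** Four points can be made for the plan.

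- **The Overview already covers it.** Its promise is not limited to particular outcomes. But it names no outcome or estimate, and the later step gives an explicit list without the primary outcome. The two passages do not agree, and an analyst would follow the detailed one. That the McNemar tests are pooled is an inference. It is the natural one, because the first step is for all participants and stratification is written out where it is meant.
- **Pooling may be the better estimator in so small a study.** With b/c = 0.20/0.10, pooling has the lower mean squared error for the refined-course change unless the bias exceeds √[0.29 × (1/30 − 1/45)] = 5.7 points. At w = 0.33 that is a version difference of about 17 points (about 14 and 19 under the other two assumptions). A 10-point difference gives only 3.3 points of bias, small beside a 19.3-point half-width. This stands as a reason to keep the pooled analysis. It is no reason to leave out the refined-course row, since nobody knows beforehand which side of the threshold the true difference lies on.
- **Aim 2 does not say which outcomes need an effect size, and the two covered outcomes are promised only change and significance.** Both are fair. Asking for an estimate on all six is a reading of part B. The primary outcome is hard to leave out on any reading.
- **PROMIS is also the weekly safety measure,** which may explain why it is split. Agreed: splitting it is not an error.

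The 0.27 to 0.40 range for w does not allow for under-recruitment or uneven loss. For example, 10 in home 1 with 20 in each other home gives 10/50 = 0.20, and 20 with 10 in each gives 20/40 = 0.50. The bias formula is unchanged.

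**Conclusion.** The concern holds. As written, the SAP specifies no refined-course estimate for four of the six Aim 2B outcomes, the primary outcome among them, and its detailed steps do not carry out its own Overview. The count comes directly from the documents. The size of any error does not: it is w × (D8 − D6), about a third of the unknown difference between the courses at the recruitment goals, in either direction, and zero if they are equally effective. The 10-point figures rest on an assumed 30-point difference, and the half-widths on assumed switching rates.

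This should be corrected, but it is a gap in specification and not a flaw in the data. The pooled tests are unaffected and the missing estimates can be produced from data already planned.

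**What to change.** **Change to the SAP.**

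- Add a third step to the primary outcome, and extend the third secondary step to JSS, ADQ and the three MBI subscales.
- For each, report the paired n and the change from baseline at the three later time points with a 95% confidence interval, separately for home 1 and for homes 2 and 3.
- For intent to leave, give the discordant counts and a small-sample interval for the paired difference in proportions. For scores, say whether the change is a mean or a median and give its standard deviation.
- Cite the homes 2 and 3 estimates as the Aim 2 effect sizes. Giving PSS and total SCS the same intervals would be a sensible small extension.
- Leave the pooled McNemar and Wilcoxon tests as they are, and label the by-version rows descriptive. If the pooled analyses have already been run, label the rows as added later.
- State that the changes are uncontrolled before-after estimates and that version is confounded with home.

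**Cost.** SAP wording and the same code on two subsets, with no new data. Aim 2 intervals are about 22% wider than pooled (17% to 29% across 15 to 20 per home), and home 1 intervals are very wide. Six measures × three time points × two versions adds 36 estimates, which invites selective reading; reporting all of them as descriptive limits that but does not remove it. None gives a between-arm effect.

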Aim 1: Determine the feasibility, acceptability, and adaptations of the CNA Wellbeing Program by conducting 8-week course in one NH with a goal of 15 CNAs, and up to 20 CNAs per NH. Evaluation will focus on a) participation (including home practice adherence); b) attendee evaluation of training; c) barriers/facilitators of participation; d) use and retention of session materials by participants; and e) recommendations for improvement.

Aim 2: Conduct a pilot test of adapted protocols and intervention in sample of 30 CNAs from 2 NHs to reexamine feasibility and acceptability. Evaluate fidelity and impact of training by measuring a) attendance, b) satisfaction with training, c) pre-post measures of self-compassion, intent to leave job, perceived stress, job satisfaction, burnout, and attitudes towards persons with dementia.

Interventions and Duration

Mindful Self-Compassion has been developed and validated in other populations as a course of eight 2.5- hour weekly sessions. A modified version of this program will be tested in Aim 2, which is also a validated version of the MSC program. This version is six, 1-hour weekly sessions. Each session begins with meditation, follows with discussion of previous week's home practice, introduction of main theme of session and new formal and informal practices. Each session will be offered in a location convenient to the NH, outside of work hours, at times convenient for participants, and offered at two different times to accommodate schedules.

Sample Size and Population

Eligibility to this study will include: Certified Nursing Assistant employed by participating nursing homes; over the age of 18; able to speak and write in English; works at NH 20 or more hours per week; expects to be employed with NH for the duration of the course; and expects to be able to attend 75% of the sessions. Up to 20 CNAs per NH will be able to participate, with a goal of 15 participants. If over 20 CNAs are interested, the study will enroll the 20 CNAs who score highest on the Screening Questionnaires' Perceived Stress Scale who are interested in participating.

STUDY TEAM ROSTER

RESEARCH TEAM			
Name	Role	Telephone	Email
[name], MPH	Principal Investigator	[contact]	[contact]
[name], MPH	Post Doctoral Fellow and Co-Principal Investigator	[contact]	[contact]
[name]	Co-Investigator, Evaluation and Research Design	[contact]	[contact]
[name]	Co-Investigator/Intervention Director		[contact]
[name]	Consulting Co-Investigator		[contact]

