self-compassion experience better interpersonal relationships and express more empathy and compassion for others.^{32,38–40} Furthermore, in nurses and nurse midwives, self-compassion protects against job burnout and compassion fatigue.^{41–43} A current training format for SC integrates it with mindfulness in an 8-session program entitled MSC which, in the limited intervention studies conducted to date, has demonstrated large, positive effects on compassion for others, stress, anxiety, depression and life satisfaction in community-based, mainly white, female, educated populations.⁴⁴ MSC interventions have also been successfully adapted for adolescents by our research team,^{45,46} and for those with diabetes.⁴⁷ MSC interventions in NH CNAs have not, however, been studied.

Because CNAs have particularly high work and life stress burdens and fewer opportunities than more educated populations to learn stress management techniques, MSC skills hold particular promise for improving outcomes. Indeed, one study of residential dementia care found that CNAs employ a range of strategies, many of which are unhelpful, such as defensiveness/shutting down, unhealthy distraction (e.g., overeating), and psychological distress (e.g., anxiety or depression); and the authors suggested that mindfulness training might have a “preventive focus” by promoting self-care.⁴⁸ Additionally, there is evidence that people with high levels of self-compassion more often use “positive cognitive restructuring” or changing one’s view of a negative situation to more a positive one,⁴⁹ a reaction that has been found to buffer against burnout in CNAs.¹⁵

Conceptual Model and Potential Impact. Figure 1 (below) illustrates our conceptual model. Among NH CNAs, work and life stress combine with low coping skills to result in high levels of perceived stress, which in turn lead to negative attitudes toward the people they care for, life and work dissatisfaction, and burnout, culminating in high rates of absenteeism and turnover, leading to impairment on the quality of care they provide. The

intervention we propose has been proven in other settings to improve performance by enhancing coping skills. If successful, MSC could be incorporated into the curricula of CNA training programs, thereby helping create a more resilient, stable, competent workforce, and one better able to provide dementia-sensitive care.

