4.1 Inclusion Criteria

Participants must meet all of the following inclusion criteria to participate in this study:

- *Certified Nursing Assistant working at 3 participating NHs*
- *Works at least 20 hours a week (on average) with participating NHs*
- *Speaks and reads English*
- *Over 18 years old*
- *Intends to work with NH for the duration of the MSC course*
- *Expects to be able to attend a majority (75%) of the sessions*

If over 20 CNAs are interested in the course, and we are not able to accommodate all whom would like to participate, an additional inclusion criteria will be scores on the Perceived Stress Scale portion of the Screening Questionnaire (see Appendix D1). The 20 CNAs with the highest scores on the PSS will be eligible for the intervention course. As of the completion of this trial, this measure was unnecessary.

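### The SAP compares the 20-hour and 6-hour versions by their separate changes and separate significance, with no between-version difference or interval, in groups planned at 15 and 30

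*SAP*

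**What the plan says.** The Analysis Overview of the SAP puts tests of change from baseline first. It then says that "analyses will consider differences in effectiveness by comparing two" approaches: the 20-hour course given in one nursing home and the 6-hour course given in two others.

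The method is the third step under Secondary Outcomes. For PSS, PROMIS and total SCS, the plan is "comparing the (a) change and (b) significance of the two sub-samples (i.e., 20-hour intervention, 6-hour intervention"). The preceding step names the only test for these scores, a Wilcoxon signed-rank test of each post-baseline time point against baseline. Standard deviations are planned for all participants together. The SAP names no standard deviation by version, and no estimate, interval or test for the difference between versions. It does not say how change and significance are to be weighed together.

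On group sizes, Protocol section 3 recruits 15 CNAs from one home for the first version. It continues: "A refined intervention will subsequently be tested in 30 CNAs from two NH settings (15 CNAs per home"). The Précis sets the limit: "Up to 20 CNAs per NH will be able to participate, with a goal of 15 participants". Missing data are not imputed, "resulting in analyses using listwise deletion of participant observations without data at each time point and for each outcome", so the analysed groups can be smaller than those recruited.

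**The concern.** A within-version p-value tests one version against its own baseline. Whether the versions differ is a question about the difference between two changes, and nothing in the plan estimates that difference with its uncertainty. Setting one significant result beside one non-significant result does not fill the gap, because the two can arise from identical true effects.

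The unequal group sizes give the error a direction. If the true change is the same and not zero, and the analysed groups stay near 1:2, the 6-hour version is more likely to be significant simply because it has more participants. A reader could conclude that the shorter course works and the longer one does not. The two observed changes, shown without an interval for their difference, do not correct that reading.

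The reach is limited. The comparison covers three secondary scores, neither aim in Protocol sections 1.1 and 1.2 includes it, and nothing in the documents makes a choice of version depend on it.

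**Working it through.** The documents contain no power calculation, effect size or standard deviation of change, so there is no planned figure to reproduce. The check asks how often significance alone disagrees when the versions truly do not differ.

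**Inputs from the documents.** Two-sided 0.05 and the Wilcoxon signed-rank test (SAP). Sizes 15 vs 30 (Protocol section 3) and 20 vs 40 (the cap of 20 per home).

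**Assumptions.** The same true change d, in SDs of the change score, in both versions; normal, independent change scores; no home effects. A third setting, 11 vs 22, assumes about 25% loss.

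**Formula.** If p1 and p2 are the probabilities that the 20-hour and 6-hour groups are significant, exactly one is significant with probability p1(1 − p2) + p2(1 − p1).

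*No true change, 15 vs 30.* The exact test sizes are 0.0479 and 0.0497, so 0.0479 × 0.9503 + 0.0497 × 0.9521 = 0.093. This disagreement is nearly symmetric.

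*d = 0.5, 15 vs 30.* Simulated power is 0.42 and 0.74. Only the 20-hour version is significant in 0.42 × 0.26 = 0.11 and only the 6-hour version in 0.74 × 0.58 = 0.43, total 0.54. A noncentral-t calculation gives 0.438 and 0.754, total 0.53.

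**All settings** (40,000 simulated trials each, exact signed-rank test): percentage with exactly one version significant.

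| n (20-hour vs 6-hour) | d = 0 | 0.2 | 0.3 | 0.5 | 0.8 | 1.0 |
|---|---|---|---|---|---|---|
| 15 vs 30 (planned) | 9 | 24 | 40 | 54 | 21 | 6 |
| 20 vs 40 (cap) | 9 | 30 | 47 | 47 | 9 | 2 |
| 11 vs 22 (assumed loss) | 8 | 19 | 31 | 54 | 40 | 20 |

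At 15 vs 30, only the 6-hour version against only the 20-hour version is 16% vs 9% at d = 0.2, 43% vs 11% at 0.5 and 20% vs 1% at 0.8.

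The only hint of effect size is in Protocol section 2, where the course "has demonstrated large, positive effects on compassion for others, stress, anxiety, depression and life satisfaction" in other populations. If large means d of 0.8 to 1.0, which is an assumption, the planned-size range is 21% down to 6%.

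**Does the side-by-side change settle it?** Among disagreeing trials at 15 vs 30 and d = 0.5, the median absolute gap between the two mean changes is 0.27 SD, although the true gap is zero. A pooled-t 95% interval for the difference includes zero in this share of the disagreeing trials:

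| d | 0 | 0.2 | 0.5 | 0.8 | 1.0 |
|---|---|---|---|---|---|
| Interval includes zero (%) | 69 | 84 | 92 | 89 | 78 |

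At every d shown, the direct interval shows no difference in most trials where significance suggests one.

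**What a direct comparison can deliver.** The half-width is t × √(1/n1 + 1/n2), in SDs of change:

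- 15 vs 30: 2.017 × 0.316 = 0.64
- 20 vs 40: 2.002 × 0.274 = 0.55
- 11 vs 22: 2.040 × 0.369 = 0.75

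The Hodges-Lehmann interval gives 0.65, 0.56 and 0.77 by simulation. At 15 vs 30, a test of the difference would have 34% power for a true gap of 0.5 SD, and 80% power only for a gap of about 0.91 SD.

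These figures ignore differences between homes. With 15 against 15 + 15, simulated coverage of the Hodges-Lehmann interval is 95.3% at an intraclass correlation of 0, and 91.7%, 86.4% and 78.5% at assumed values of 0.02, 0.05 and 0.10.

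**The case against.** The strongest case is about weight. This is a small feasibility study with no randomised comparison. Neither aim compares versions, and the primary outcome is untouched. Version is fixed by nursing home, so no analysis of these data could attribute a difference to course length. The SAP only promises to consider differences, lists change before significance, and states no rule for declaring one. On that view, a sentence saying that significance is not used to compare versions would be enough.

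Most of these facts are right. They limit the importance of the point, and they mean the percentages above are disagreement rates for the significance element, not error rates of the plan. They do not make the comparison valid. The SAP poses the question and names compared significance as half of the answer. Protocol section 1.2 says the pilot is to estimate effect size for a later randomised trial, which calls for estimates with intervals.

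Four narrower objections also stand in part:

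- The 6-hour group's advantage needs a nonzero true change and analysed groups near 1:2; the planned sizes are recruitment goals.
- At d = 0 the direct interval itself excludes zero in about three of ten disagreeing trials. That is a result of looking only at disagreeing trials; its overall coverage is 95% if homes do not differ.
- The simulation used continuous normal changes, whereas PSS and PROMIS sums are bounded integers with ties.
- A difference in mean change with its interval would also serve, because the SAP summarises these scores as means.

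**Conclusion.** The concern holds and should be fixed. For its second question the SAP specifies a comparison that cannot show whether the versions differ. That conclusion follows from the text and needs no assumed effect size.

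The size does depend on assumptions: equal true change in both versions, normal change scores, no home effects, and the planned numbers analysed. On those terms significance disagrees in 6% to 54% of trials over the d values examined, and at nonzero d mostly in favour of the 6-hour group. The consequence is confined to how three secondary scores are read.

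**What to change.** Remove significance as a basis for comparing versions. For PSS, PROMIS and total SCS at each post-baseline time point, report the between-version difference in change from baseline, as a Hodges-Lehmann shift with a 95% confidence interval and no between-version p-value. Show each version's analysed n and baseline value beside it.

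The SAP should also state that:

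- the comparison is descriptive and not adjusted for multiplicity;
- version is nested in nursing home and cohort, so a difference cannot be attributed to course length;
- the interval's coverage assumes no home effects;
- an interval that includes zero does not show equivalence.

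If the analysis has already been run, the new contrast should be labelled post hoc. The wording suggests that it has: the SAP says "all analyses were conducted in Stata 16.1", and Protocol section 4.1 says "As of the completion of this trial, this measure was unnecessary" of the stress-score selection rule.

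The cost is a few sentences and up to nine contrasts (3 scores × 3 time points) on data already collected. The intervals will be wide. That makes the uncertainty visible, but it does not remove the confounding of version with home.
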